## **1 Introduction**

This statistical analysis plan (SAP) documents the statistical methodology and data analysis algorithms and conventions to be applied for statistical analysis and reporting of efficacy and safety data of trial 31-10-270. The first approved protocol, dated 30 Mar 2010, and its amendments (amendment 1 - 23 Nov 2010, amendment 2 - 08 Apr 2013, amendment 3 - 11 Apr 2013, amendment 4 - 08 Jul 2015) are taken into consideration in developing this SAP.

## **2 Trial Objectives**

### **2.1 Primary Objective**

To continue to provide aripiprazole intramuscular (IM) Depot treatment (400 mg or 300 mg) to subjects with schizophrenia completing the 52-week, open-label safety and tolerability trial 31-08-248 (hereafter referred to as trial 248). Subjects can receive this treatment until aripiprazole IM Depot is commercially available in any dosage [including generic formulation(s)] in the country that the trial is being conducted or until the trial end date of 31 Dec 2018 is reached.

### **2.2 Secondary Objective**

The secondary objective of this trial is to collect long-term safety data on aripiprazole IM Depot in addition to what was collected in trial 248 (52-weeks).

## **3 Trial Design**

This is an open-label, multicenter rollover non-comparative trial. The adult subjects with schizophrenia who completed aripiprazole IM Depot treatment in trial 248 are allowed to enroll this trial. No subject who discontinued or did not complete trial 248 are allowed to enroll in this trial. The trial design is presented in [Figure 3-1](#) and [Figure 3-2](#).

Eligible subjects enter this trial directly after completing the end of treatment visit (week 52) of trial 248. The end of treatment evaluations conducted at the last trial visit for trial 248 serve as the baseline evaluations for this trial. Subjects continue to receive aripiprazole IM Depot every month as a continuation of their previous monthly dose in trial 248. The monthly dose can be modified, either reduced from 400 mg to 300 mg to address tolerability or increased from 300mg to 400mg to address efficacy, at the discretion of the investigator.

Following the baseline visit, subjects receive monthly injections and at the same visit, adverse events (AEs) and concomitant medications are recorded and the Columbia

Suicide Severity Rating Scale (C-SSRS) are completed. Every 3 months, all of the monthly assessments are completed along with a urine pregnancy test for women of childbearing potential (WOCBP). Every 6 months, all of the 3-month assessments are completed along with the Clinical Global Impression - Severity (CGI-S) scale, vital signs, and extrapyramidal symptoms (EPS) assessments (including the Abnormal Involuntary Movement Scale [AIMS], Simpson-Angus Scale [SAS], and Barnes Akathisia Rating Scale [BARS]). At the 12-month visit, all of the 6-month assessments are completed along with clinical laboratory tests and assessments of body weight, height, and waist circumference.

Urine drug screening and blood alcohol testing are obtained at baseline and can be re-obtained at the investigator's discretion at any time during the trial. A Visual Analog Scale (VAS) for subject-reported rating of pain at the most recent injection site and the investigator's assessment for pain, redness, induration, and swelling of the most recent injection site are performed at baseline and may be reassessed at the discretion of the investigator. Clinical laboratory tests, physical examination, and electrocardiogram (ECG) obtained at baseline may also be performed at the discretion of the investigator based on clinical necessity.

A Trial Completion visit or Early Termination visit ( $-2/+10$  days) includes the following assessments: C-SSRS, AEs, concomitant medications, a urine pregnancy test for WOCBP, CGI-S, vital signs, EPS assessments (AIMS, BARS, SAS), clinical laboratory tests, and body height and weight.

A 30-Day Post Treatment Follow-up phone call is made 30 days ( $\pm 3$  days) after it has been determined that the subject no longer participates in this trial and includes questions about any AEs that have occurred and any concomitant medications taken since the last visit

The subject population is comprised of subjects who have completed Trial 248 and in the investigator's judgment may benefit from continued participation in an aripiprazole IM Depot trial, in countries where aripiprazole IM Depot is not commercially available. It is anticipated that 500 to 800 subjects from estimated 250 sites in trial 248 enroll in this trial.

Study Entry	Open Label IM Depot Treatment	Follow up

Study 248 Completers only
	
Every Month: Injection visits, C-SSRS, AEs, & concomitant medications
 
Every 3 months: CGI-S, vital signs, urine pregnancy test, optional drug and alcohol testing
 
Every 6 months: Injection site assessments
 
Every 12 months: Clinical laboratory tests, PE, ECG, body height & weight, BMI, and waist circumference
	
One 6-month post End of Study

Week 52 Visit of Study 248 = Baseline for Study 270
	
Injection visit window => 28 (-2/+10) days
 
Assessment visit windows => -2/+10 days
	
-2/+10 days

Note: The 3-month, 6-month, and 12-month visits include assessments from the previous visit. For example, the 3-month visit includes all of the monthly visit assessments in addition to the 3-month visit assessments.

Figure 3-1 Trial 31-10-270 Trial Design Schema Prior to Amendment 4

Trial Entry	Open-label IM Depot Treatment	Follow-up

Trial 248 Completers only
	
Every month: Injection, C-SSRS, AEs, and concomitant medications
 
Every 3 monthsa: Urine pregnancy test for WOCBP
 
Every 6 monthsa: CGI-S, vital signs, and EPS assessments (AIMS, BARS, SAS)
 
Every 12 monthsa: Clinical laboratory tests, body weight and height, and waist circumference
	
One 30-day post End of Study phone call - AEs and concomitant medications


Week 52 Visit of Trial 248 = Baseline for Trial 270
	
Injection visit window = 28 (-2/+10) days
 
Assessment visit window = -2/+10 days
	
± 3 days

aThe 3-month, 6-month, and 12-month visits include assessments from the previous visit. For example, the 3-month visit includes all of the monthly visit assessments in addition to the 3-month visit assessments. A Trial Completion or Early Termination visit will also be performed.

Figure 3-2 Trial 31-10-270 Trial Design Schema in Amendment 4

## **4 Sample Size and Power Justification**

In this open-label, single arm rollover trial, no formal sample computations were employed. The anticipated number of subjects from Trial 248 that is predicted to enroll in this trial is approximately 500 to 800.

## **5 Statistical Method**

### **5.1 Data/Data Sets Specifications**

#### **5.1.1 Data Sets Analyzed**

The following analysis samples are defined for this trial:

- Enrolled Sample: All subjects who sign the informed consents form for the trial and enter the trial.
- Safety Sample: All subjects who receive at least one dose of open-label aripiprazole IM depot.
- Efficacy Sample: All subjects who enter and have at least one post-baseline efficacy evaluation.

Due to the open-label single-arm nature of the trial, all endpoints will be summarized using descriptive statistics. Continuing variables will be tabulated for frequency, mean, median, standard deviation (SD), maximum and minimum. Categorical variables will be tabulated for frequency and percentage. No formal statistical analyses are planned due to the open-label nature of this trial. Subjects who enrolled in this trial rolled over directly from Trial 248. Subjects who enrolled in Trial 248 either rolled over from Trial 31-07-246 or Trial 31-07-247, or directly entered Trial 31-08-248 as *de novo* subjects (i.e., subjects never enrolled in Trial 31-07-246 or 31-07-247). The data will be summarized by enrollment source into Trial 248 as well for all subjects.

#### **5.1.2 Definition of Baseline and Last Visit**

Baseline is defined as the last visit with available data in Trial 248. The last visit is defined as the last visit with available data at the completion or on/before early termination. These definitions apply to all efficacy analysis and safety analysis.

## **5.2 Disposition of Subjects**

Disposition of subjects for the enrolled sample will be summarized by region, country and center. Subject duration by month and reason for discontinuation will be tabulated for the enrolled sample. Subjects who are evaluated at last scheduled visit during the treatment period are defined as completers. Subjects who are evaluated at the last scheduled visit during the treatment period are defined as completers, i.e., subjects who have their last scheduled visit, or who discontinue due to the commercial availability of trial drug in the country are defined as completers.

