3.7 Stopping Rules, Withdrawal Criteria, and Procedures

3.7.1 Entire Trial or Treatment Arm(s)

The sponsor should be notified promptly if the trial is terminated at your site. If the sponsor decides to terminate or suspend the trial for safety or unanticipated other reasons or if aripiprazole IM Depot becomes commercially available in the country of the study site, the sponsor will promptly notify investigators, IRBs/IECs, and regulatory authorities as required by the applicable regulatory requirements.

The sponsor will terminate the study in countries where aripiprazole IM Depot becomes commercially available (including generic formulation[s]), the commercial availability of aripiprazole IM Depot is terminated by the sponsor, or if the study end date of 31 Dec 2018 is reached.

If the sponsor terminates the study prior to 31 Dec 2018 for any reason other than commercial availability, investigators in some countries where the sponsor has limited or delayed commercialization plans, or where no commercialization activity is anticipated, may be eligible to participate in a managed access program until aripiprazole IM Depot is commercially available in their country or until 31 Dec 2018. Availability and requirements of such a program varies by jurisdiction, and would only be an option for subjects who were receiving aripiprazole IM Depot in the current study, and who in the physician's opinion, may benefit from continued treatment with aripiprazole. To gain access to aripiprazole IM Depot for eligible subjects via a managed access program, each physician will be responsible for gaining appropriate local regulatory approvals, which will be granted by authorities on a case-by-case basis. The sponsor makes no guarantee that such a program is available or approvable in all of the jurisdictions where the study is conducted.

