3.9 Definition of Completed Subjects

The treatment period is defined as the time period during which subjects are evaluated for primary and/or secondary objectives of the trial irrespective of whether or not the subject actually received all doses of the study medication. Subjects who are evaluated at the last scheduled visit during the treatment period will be defined as trial completers. Subjects who have their last visit by 31 Dec 2018, because they have reached the end of the study, will be defined as completers. For purposes of this trial, subjects who discontinue due to the commercial availability of study drug in the country where the study is being conducted will be defined as completers. In addition, subjects in countries where a managed access program is available for continued treatment with aripiprazole at the time of trial closure in their respective country, regardless of whether they transition to a managed access program, will also be defined as completers. Protocol-specified post-treatment follow-up contacts will not qualify as “last scheduled” visit.

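### The SAP's completer rule omits the managed-access completers that the protocol defines; an early country closure with such a program could understate completion in the disposition tables

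*SAP*

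**What the plan says.** Protocol section 3.9 gives four ways to be a completer:

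- Last scheduled visit: "Subjects who are evaluated at the last scheduled visit during the treatment period will be defined as trial completers".
- Study end date: "Subjects who have their last visit by 31 Dec 2018, because they have reached the end of the study, will be defined as completers".
- Commercial availability: "subjects who discontinue due to the commercial availability of study drug in the country where the study is being conducted will be defined as completers".
- Managed access: "subjects in countries where a managed access program is available for continued treatment with aripiprazole at the time of trial closure" in their country, who, "regardless of whether they transition to a managed access program, will also be defined as completers".

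SAP section 5.2 states the general last-scheduled-visit rule twice. After the second statement it spells out the meaning with an i.e. that names two cases only. One is having the last scheduled visit; the other is the group "who discontinue due to the commercial availability of trial drug in the country are defined as completers". Managed access appears neither there nor elsewhere in the SAP text supplied. SAP section 1 lists Amendment 4 (08 Jul 2015) among the protocol versions taken into account. Protocol Appendix 14 shows that this amendment added the managed-access sentence to section 3.9.

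SAP 5.2 tabulates disposition and reasons for discontinuation for the enrolled sample. SAP Appendix 4 assigns these to tables CT-1.1, CT-1.2 and CT-2, with listings including DREAS-1 and PDATA-3.

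**The concern.** The two documents define the same term differently, and the SAP gives no reason for the difference. An i.e. reads as a complete list, so a programmer who follows the SAP would leave out a group that the protocol counts as completers.

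The primary objective of this rollover trial is continued supply of treatment. Who stayed to the end, and why others left, is therefore a descriptive result that readers will look for. A subject still on treatment when the sponsor closes a country has not left by choice or for a clinical reason, yet the literal SAP rule would place that subject among the discontinued. The class is defined by country, so any misclassification would fall in whole countries and show most clearly in CT-1.2, which breaks disposition down by region, country and center.

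**Working it through.** The documents state no completion rate, so there is no figure to reproduce. The check is a comparison of the two definitions, followed by a formula for the size.

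**Step 1: match the routes.**

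| Route to completer status | Protocol 3.9 | SAP 5.2 |
|---|---|---|
| Last scheduled visit of the treatment period | Yes | Yes |
| Last visit by 31 Dec 2018 because the study has ended | Yes | Not named, but fits the last scheduled visit |
| Discontinued because the drug became commercially available | Yes | Yes |
| In a country with a managed access program at closure there | Yes | Not named |

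**Step 2: could a route named in the SAP cover the last row?**

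- *Commercial availability.* No. Protocol section 3.7.1 introduces managed access with the condition "If the sponsor terminates the study prior to 31 Dec 2018 for any reason other than commercial availability". A closure that meets this condition is by definition not a commercial-availability closure.
- *Last scheduled visit.* Not clearly. Protocol section 3.6.1.2 schedules monthly visits through Study Month 104, and a subject in a country closed early need not have got that far. If the phrase already covered any administrative closure, neither document would need a separate commercial-availability clause, and the protocol would not need to add managed access as a further class.

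**Step 3: direction.** Every SAP route is also a protocol route, and the protocol has one more. The SAP completer count therefore cannot exceed the protocol count. Any error understates completion relative to the protocol.

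**Step 4: size.** Let N be the number enrolled and k the number who are completers only through managed access.

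Shortfall in completion = k / N, and the discontinued proportion rises by the same amount.

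N is anticipated to be 500 to 800 (Protocol 7.5; SAP 4). The documents do not give k. The values of k below are assumptions, chosen only to show the scale:

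| k (assumed) | N = 500 | N = 800 |
|---|---|---|
| 0 | 0 points | 0 points |
| 5 | 5/500 = 1.0 point | 5/800 = 0.6 points |
| 25 | 25/500 = 5.0 points | 25/800 = 3.1 points |
| 50 | 50/500 = 10.0 points | 50/800 = 6.3 points |

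**Step 5: reach.** SAP section 5.1.1 defines the enrolled, safety and efficacy samples without reference to completion. The primary measures in Protocol section 7.3 are adverse events, serious adverse events and discontinuations due to adverse events; none turns on completer status. The CGI-S summaries do not use it either.

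**The case against.** The strongest reply is that the mismatch may never matter. Managed access arises only if the sponsor ends the study early for a non-commercial reason. Even then it is possible only in some countries, and Protocol 3.7.1 declines to guarantee it. Nothing in the documents shows that such a closure took place or was planned. This stands, and it is why the effect is conditional.

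A second reply is that practice may already avoid the error. Subjects leaving at closure have a Study Completion or Early Termination visit (Protocol 3.6.1.6), which could be read as their last scheduled visit. PDATA-3 lists trial completion status; if sites record that under Protocol 3.9 and the tables use it, they will agree with the protocol. Either is possible, but the SAP specifies neither, so two programmers could reach different completion rates from the same data.

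A third reply is that the tables would still show why subjects left. CT-2 gives reasons for discontinuation and DREAS-1 lists them by subject. This stands in part. A reader might infer that closures would be indistinguishable from clinical drop-out, but the documents do not list the reason categories, so that is not shown. The completer count would still be wrong against the protocol.

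**Conclusion.** The SAP's rule conflicts with the protocol as written and should be aligned. The consequence is conditional. It needs an early country closure on non-commercial grounds, a managed access program available there, subjects still in the trial at that point, and tables built from the literal SAP sentence. Where all four hold, completion is understated by k/N; otherwise the effect is zero.

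A reader might infer that completion will be understated by some definite number of percentage points. The documents do not support this, because they give neither k nor any basis for estimating it. Nor do they support a reading that the safety or efficacy results are at risk. The matter is confined to CT-1.1, CT-1.2, CT-2 and the related listings.

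**What to change.** Replace the completer wording in SAP 5.2 with the full definition in Protocol 3.9, including the managed-access class and the 31 Dec 2018 case.

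Specify how the managed-access class is derived. It needs the date of trial closure in each country, whether a program was available there at that date, and whether the subject was still in the trial. The last condition matters: read literally, the protocol sentence covers subjects by country. A country flag alone could turn earlier withdrawals for adverse events, withdrawn consent or loss to follow-up into completers, and so overstate completion.

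The cost is one SAP paragraph, a short country-level table that the sponsor should be able to supply, and one derivation. No new data are needed from subjects. Showing completion by route in CT-1.1 and CT-2 would help the reader but is optional.

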## **5.3 Demographic and Baseline Characteristics**

Baseline and demographic characteristics will be summarized using descriptive statistics for the enrolled sample. These characteristics including age, race, ethnicity, gender, weight, height and body mass index (BMI), will be tabulated for the enrolled sample.

## **5.4 Efficacy Analysis**

Change from baseline in CGI Severity (CGI-S) score will be summarized by scheduled visit using descriptive statistics for the efficacy sample. CGI-S score (range 1-7) are directly derived from CGI-S panel.

## **5.5 Safety Analyses**

### **5.5.1 Adverse Events**

All adverse events (AEs) are coded by system organ class and Medical Dictionary for Regulatory Activities (MedDRA) preferred term (Version 21.0 or later). A treatment-emergent AE (TEAE) is defined as an AE which starts after start of trial medication (Aripiprazole IM Depot), or an AE continues from baseline and becomes serious, worsening, trial drug-related or results in death, discontinuation, interruption or reduction of trial medication during this trial. All ongoing AEs and clinically significant AEs from

Trial 248 are recorded as Medical History for this trial. If the AE increases severity or frequency during this trial period, a new AE are recorded. The incidences of the following treatment-emergent adverse events (TEAEs) will be summarized for the safety sample:

- TEAEs by severity
- Potentially drug-related TEAEs
- TEAEs with an outcome of death
- Serious TEAEs
- Discontinuations due to TEAEs

Listing and incidences of AEs described above are tabulated for the safety sample.

Deaths, SAEs, and AEs leading to discontinuation from trial or trial treatment are listed for the enrolled sample. In addition, incidences of TEAEs will be provided for the following subgroup analyses: region (US, non-US), sex (male, female), race (Caucasian, Black or African American, American Indian or Alaska Native, Asian, other), age (< 45 years old,  $\geq 45$  years old), ethnicity (Hispanic or Latino, not Hispanic or Latino), and BMI at baseline ( $\leq 28$  kg/m^2,  $> 28$  kg/m^2).

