3.6.1.1 Baseline

The baseline visit for Study 270 (which is the Week 52 visit of Study 248) and the first injection for Study 270 must occur within 4 weeks (which is defined as 28 [-2/+10] days) of the last injection in Study 248. At this visit, subjects will sign an Informed Consent for Study 270 and their eligibility will be confirmed.

The Study 248 Week 52 assessments will also serve as the baseline assessments for Study 270: CGI-S; C-SSRS; EPS assessments (AIMS, SAS, BARS); injection site pain assessed by the subject using VAS; investigator's injection site assessment for pain, redness, swelling, and induration; body weight and height; BMI; waist circumference; AEs; clinical laboratory tests; vital signs; physical exam; ECG; urine pregnancy test for WOCBP (see [Section 5.4](#) for the definition of WOCBP); urine drug screen; blood alcohol test; and concomitant medications (see [Table 3.6-1](#)). All ongoing AEs and clinically significant AEs from Study 248 will be recorded as Medical History of Study 270; please refer to the Operations Manual or case report form (CRF) Completion Guidelines for additional detail.

In addition to the assessments, the baseline visit will also include the first aripiprazole IM Depot injection for Study 270.

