5.1 Definitions

An adverse event (AE) is defined as any new medical problem, or exacerbation of an existing problem, experienced by a subject while enrolled in the study, whether or not it is considered drug-related by the investigator.

A serious AE (SAE) includes any event that results in any of the following outcomes:

- Death.
- Life-threatening, ie, the subject was, in the opinion of the investigator, at immediate risk of death from the event as it occurred. It does not include an event that, had it occurred in a more severe form, might have caused death.
- Persistent or significant disability/incapacity.
- Requires in-patient hospitalization or prolongs hospitalization.
- Congenital anomaly/birth defect.
- Other medically significant events that, based upon appropriate medical judgment, may jeopardize the subject and may require medical or surgical intervention to prevent one of the outcomes listed above, eg, allergic bronchospasm requiring intensive treatment in an emergency room or home, blood dyscrasias or convulsions that do not result in hospitalization, or the development of drug dependency or drug abuse.

Non-serious adverse events are all AEs that do not meet the criteria for a "serious" adverse event.

Immediately Reportable Event (IRE):

- Any serious adverse event.
- Any AE that necessitates discontinuation of study drug.
- Potential Hy's Law cases (Any increase of AST or ALT \geq three times the upper normal limit with \geq two times increase in total bilirubin).
- Pregnancies are also defined as IREs. Although normal pregnancy is not an adverse event, it will mandate drug discontinuation and must be reported on an IRE form to Otsuka Pharmaceutical Development and Commercialization, Inc. (OPDC). Pregnancy will only be documented on the AE-CRF if there is an abnormality or complication.

Protocol 31-10-270

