7.3 Primary Outcome Measures

In this safety and tolerability study, the primary measures are (1) frequency and severity of adverse events, (2) frequency and severity of serious adverse events (including adverse events related to laboratory abnormalities), and (3) rates of discontinuation from study due to adverse events.

Safety and tolerability data will be summarized as follows: Incidence of adverse events and serious adverse events (with severity grades) will be tabulated by Medical Dictionary for Regulatory Activities (MedDRA) terms; similarly, incidence of discontinuations due to AE will be tabulated by MedDRA terms.

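### The SAP 5.5.1 rule for re-recording carried-over Trial 248 AEs is narrower than its TEAE definition, so unchanged events that become drug-related or lead to discontinuation, interruption or dose reduction may be missed

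*SAP*

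**What the plan says.** The TEAE definition in SAP 5.5.1 has two parts: AEs that start after the first trial injection, and continuing AEs that change in some listed way. The second part reads: "an AE continues from baseline and becomes serious, worsening, trial drug-related or results in death, discontinuation, interruption or reduction of trial medication". That is seven triggers: serious, worsening, drug-related, death, discontinuation, interruption and reduction.

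Protocol 3.6.1.1 says where such events are held at entry: "All ongoing AEs and clinically significant AEs from Study 248 will be recorded as Medical History of Study 270". SAP 5.5.1 repeats this and adds the rule for opening a fresh record: "If the AE increases severity or frequency during this trial period, a new AE are recorded". No other re-recording rule appears in either document. Protocol 3.6.1.1 follows its medical-history sentence with a referral: "please refer to the Operations Manual or case report form (CRF) Completion Guidelines for additional detail". Those manuals are not among the documents reviewed.

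The third primary measure in Protocol 7.3 is "rates of discontinuation from study due to adverse events". In SAP Appendix 4, CT-8.6.1 to CT-8.6.3 tabulate TEAEs that led to stopping study medication, CT-8.3.1 to CT-8.3.3 tabulate potentially drug-related TEAEs, and CT-2 tabulates reasons for discontinuation.

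**The concern.** The definition and the recording rule sit in one paragraph but do not match. The definition expects a continuing event to enter the tables for reasons other than worsening. The recording rule supplies a new record only for a rise in severity or frequency. Take a subject who enters with mild akathisia that stays mild, and who later stops treatment or has the dose reduced because of it. The definition makes this a TEAE. Read literally, the recording rule leaves it on the medical-history page.

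Two features of the trial make this worth settling. Every subject comes straight from Trial 248 on the same product, so some will bring ongoing AEs. The design also allows a reduction from 400 mg to 300 mg for tolerability (Protocol 3.1 and 3.2), so the reduction trigger is a foreseeable event. At stake are the drug-related and discontinuation tables, the second of which reports a primary measure.

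**Working it through.** The plan gives no figure to reproduce: the trial is descriptive and has no formal sample-size calculation. The check takes each of the seven triggers, assumes a carried-over event, and looks for a stated route into the AE data.

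| Trigger | SAP 5.5.1 re-recording rule | Route in the protocol | Result |
|---|---|---|---|
| Worsening | Named (severity or frequency) | AE definition includes exacerbation (5.1) | Covered |
| Serious | Not named | Outcome-based SAE definition (5.1) and duty to enter all AEs on the CRF (5.2) | Largely covered |
| Death | Not named | As for serious | Largely covered |
| Discontinuation | Not named | Reportable on the IRE form (5.1, 5.3), which the protocol says is not the AE CRF | Doubtful |
| Drug-related | Not named | Causality is described for AEs (5.1), not for medical-history entries | None stated |
| Interruption | Not named | Unscheduled dosing is explained on the CRF (3.11), but as a dosing record | None stated |
| Reduction | Not named | None found | None stated |

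Tally: 1 covered + 2 largely covered + 1 doubtful + 3 with no stated route = 7.

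The last four rows turn on the protocol's AE definition: "any new medical problem, or exacerbation of an existing problem, experienced by a subject while enrolled in the study". A condition already present at entry and unchanged since is neither new nor an exacerbation, so the general duty in Protocol 5.2 to record all AEs does not clearly reach it. Protocol 3.6.3.3.1 (examination findings absent at baseline) and 5.1 (laboratory changes from baseline) follow the same logic. Serious events differ because that definition turns on outcome: "A serious AE (SAE) includes any event that results in any of the following outcomes".

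The consequences differ by trigger. A missing discontinuation record affects CT-8.6.x, and a missing drug-related record affects CT-8.3.x. Appendix 4 has no separate table for interruption or reduction, so those losses would fall in the overall TEAE tables (CT-8.2.x), and in CT-8.3.x if the event was also judged related.

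On size, let *p* be the true proportion discontinuing for an AE and *f* the share of those discontinuations due to unchanged carried-over events that were never re-recorded. CT-8.6.x would then show *p* × (1 − *f*). The documents give neither value. As an illustration on assumed values only, take 600 subjects (inside the anticipated 500 to 800) and *p* = 5%:

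- 600 × 0.05 = 30 discontinuations
- *f* = 0: none lost, rate 5%
- *f* = 5%: 30 × 0.05 = 1.5 lost, rate 5% × 0.95 = 4.75%
- *f* = 20%: 30 × 0.20 = 6 lost, rate 5% × 0.80 = 4.0%

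This shows the direction and how the loss scales. It is not an estimate.

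**The case against.** The tempting stronger reading is that these events, serious ones included, cannot be counted at all because a new AE is opened *only* on worsening. The documents do not support that. The SAP sentence gives a sufficient condition and does not contain the word *only*. The manuals named in Protocol 3.6.1.1 may add the missing routes. Serious and fatal events have their own route. All of this stands, and it limits the point to four triggers and to *may be missed*.

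A reader might also infer that the primary measure as a whole is undercounted. Against that, Protocol 7.3 speaks of AEs rather than TEAEs. SAP 5.2 tabulates reasons for discontinuation in the enrolled sample, and withdrawal for an AE is a named criterion in Protocol 3.7.3. Such a withdrawal can appear in CT-2 whatever the re-recording rule does. This stands too, but it leaves two tables that can disagree with no stated rule for reconciling them. Only CT-8.6.x gives the MedDRA breakdown that Protocol 7.3 asks for.

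The IRE duty in Protocol 5.2 is additional to CRF recording and does not replace it. That helps for discontinuation if the site already regards the condition as an AE of this trial, which is the unclear step.

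Finally, it might be inferred that carried-over events are a main source of tolerability withdrawals here. The documents do not show this. Entrants completed Trial 248, were judged likely to benefit, and are excluded if known to be intolerant of aripiprazole. Many events that come to force withdrawal will also have worsened, and so will have been re-recorded.

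**Conclusion.** The point holds as a mismatch between two stated rules. Of the seven continuing-event triggers, three (drug-related, interruption, reduction) have no stated route from medical history to an AE record when the event has not worsened, and a fourth (discontinuation) is doubtful. Followed literally, the rules can undercount CT-8.3.x and CT-8.6.x, and so the MedDRA tabulation of the third primary measure. They cannot overcount it.

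The size cannot be computed from the documents, and it could be nil if the Operations Manual or CRF Completion Guidelines already require re-recording on these triggers. The conclusion rests on the protocol and SAP text alone and on reading the AE definition as excluding an unchanged condition. It does not extend to serious or fatal events.

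**What to change.** 1. In SAP 5.5.1, and in the CRF guidance if it says the same, make the recording rule match the definition: a new AE record whenever a carried-over condition meets any of the seven triggers. Alternatively, state how medical-history entries are linked to the AE dataset when a trigger is met.
2. For data already collected, reconcile disposition (CT-2, PDATA-3), trial medication (PDATA-7) and medical history (PDATA-8) against the AE records. Where a carried-over event led to discontinuation, interruption or reduction and has no AE record, add it to the TEAE tables and, for discontinuations, to CT-8.6.x. Flag these as derived.
3. State how differences between CT-2 and CT-8.6.x are to be explained. Some may arise simply because CT-2 uses the enrolled sample and CT-8.6.x the safety sample.

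The listings are already planned, so the cost is a change of a sentence or so and one reconciliation. The AE discontinuation rate may rise slightly. One gap will remain: an unchanged event later judged drug-related, with no effect on dosing or disposition, leaves no trace in those listings. The report should say so.
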